#### **5. LAY LANGUAGE SUMMARY OR SYNOPSIS (no more than one paragraph)**

We will develop and pilot test a culturally tailored, trauma-informed smartphone app, called *LinkPositively*, for Black WLHA affected by interpersonal violence. Core components of *LinkPositively* include: a) Virtual Peer Navigation that includes phone and text check-ins and 4 weekly one-on-one video sessions to build skills to cope with barriers and navigate care; b) Social Networking platform to receive peer support; c) Educational and Self-care database with healthy living and self-care tips; d) GPS-enabled Resource Locator for HIV care and ancillary support service agencies; and e) ART self-monitoring and reminder system. Guided by the Theory of Triadic Influences and Syndemic Theory, the study will be conducted in 2 phases with corresponding aims. In Phase 1 (Aim 1), 4 focus groups with Black WLHA with experiences of interpersonal violence, one focus group with peer navigators, and 4-6 key informant interviews with providers will be conducted to determine which app features, content, and functions are most likely to support downloading, initiating use, and sustaining engagement over time. Aim 1 will culminate in usability testing by Black WLHA affected by interpersonal violence (n=8), to finalize intervention components and procedures. In Phase 2 (Aim 2), we will pilot test *LinkPositively* to assess feasibility and acceptability and determine preliminary effects of the intervention on HIV care outcomes (i.e., retention in care, ART adherence, viral suppression) and mechanism of change variables (i.e., social support, self-efficacy). Through a randomized control trial (RCT), participants will be randomly assigned to either the intervention arm (n=40) or control arm (Ryan White standard of care, n=40), with follow-up at 3- and 6- months. This study will benefit the advancement of HIV prevention science by harnessing technology to promote engagement in HIV care, while improving social support through peers and social networking—all under the auspices of being trauma-informed for Black WLHA with experiences of interpersonal violence.

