##### **Aim 2: Conduct a pilot randomized controlled trial to assess the feasibility, acceptability and preliminary impact of the *LinkPositively* intervention for Black WLHA affected by interpersonal violence, in preparation for a large-scale R01.**

Eighty Black WLHA ever experiencing interpersonal violence will be randomly assigned (1:1) to receive *LinkPositively* or standard of care Ryan White services, with self-reported, biological, and clinical outcomes collected at baseline, 3- and 6-month follow-up visits. Intervention use data will be collected throughout the intervention period to examine feasibility, acceptability, and the associations between components used and study outcomes. Primary outcomes are retention in HIV care, ART adherence, and viral suppression, whereas socio-structural mechanism of change variables are social support and

activation of social support networks, self-efficacy, and utilization of ancillary support services. To minimize recall bias and/or social desirability bias, that may occur with the use of audio computer-assisted self-interviews, we will use objective data to measure the main outcomes. Retention in HIV care and viral suppression will be based on medical record data and ART adherence will be measured using hair samples assayed for tenofovir and emtricitabine. The proposed study will benefit the advancement of HIV prevention science by harnessing mobile technology to promote retention in HIV care and ART adherence among US Black WLHA affected by interpersonal violence and co-occurring adverse mental health and substance abuse – an underserved, marginalized population. If the LinkPositively intervention is efficacious through an eventual R01 mechanism, it will change the paradigm for addressing the unique HIV treatment needs for Black women dually affected by HIV and interpersonal violence.

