### **Intervention Trial:**

**Treatment Conditions.** Following the Baseline Visit, participants will be randomized at a 1:1 ratio to an intervention arm or control arm. The Biostatistician team will generate the randomization sequence to ensure that randomization occurs independent of the core research team. Participants will be informed of their study group assignment immediately after completion of their baseline survey.

**Control Arm.** Women assigned to the control arm will be connected with and will receive self-directed (non-Peer Navigation supported) treatment as usual at agencies and institutions in San Diego, Los Angeles, Alameda, Oklahoma City, or Tulsa County following the Ryan White HIV/AIDS Program standard of care (i.e., referrals to physical, dental, and mental health services; medical case management; and ancillary services [e.g., alcohol/substance use recovery, family support]). Women who are not already receiving services and do not have other means of receiving services or are not under medical case management elsewhere will be referred to care. Alternatively, women may request case management services via Ryan White HIV/AIDS Program at a preferred location.

Using the Ryan White standards of care, goals will be set to create an individual care plan related to medical care, housing, financial, and other resources as needed. Referrals will be made to appropriate services (e.g., primary care, housing, benefits counseling, transportation, food, legal services, support services) based on intake interview. Women who require a higher level of care (e.g., significant mental health concern, at risk or falling out of care) and do not have other means of receiving services or are not under medical case management elsewhere may request case management services via Ryan White HIV/AIDS Program in San Diego, Los Angeles, Alameda, Oklahoma City, or Tulsa County.

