5. **Virtual Peer Navigation.** Study participants will be matched with a trained, trauma-informed virtual PN—based on shared lived experiences —who deliver this component of the intervention using a HIPPA-compliant videoconferencing software, Zoom Conference. Participants can link to their Zoom PN meeting by clicking on a link within the LinkPositively app to connect with their matched PN. First, the assigned PNs will conduct an intake/needs assessment and create goals, case plan with their assigned clients, discuss ways to maximize the effectiveness of the LinkPositively app, and link clients to HIV medical care and ancillary support services, as well as other local resources. Next, a total of 5 structured PN sessions will occur over a five-week period. Two sessions will focus on emotional intelligence: (a) increasing emotional awareness, understanding trauma and other co-occurring syndemic conditions (e.g., mental health disorders, substance abuse) including emotional responses to them, and (b) cultivating emotional regulation and distress tolerance, specific to PTSD following interpersonal violence. The third session will focus on activating social support networks, specifically, identifying and changing relationship patterns (i.e., understanding negative relationship patterns based on interpersonal violence experiences and other syndemic conditions and identification of alternative and more adaptive interpersonal schemas). The fourth session will address how interpersonal violence (e.g., power and control dynamics, disclosure of violence) can impact existing socio-structural barriers (e.g., HIV stigma, medical mistrust) and developing strategies to obtain care and support while accounting for these issues. The fifth and final session will focus on aspects of medical mistrust and discrimination in the context of HIV care and discuss skills to improve patient-provider communication. Each session will last 1 hour and occur at a convenient time for the participant. Women will be able to text/call their PN during and after the 5-week period if they have questions or seek to debrief after sessions or appointments. In the backend of the website app, PNs will enter case notes on PN sessions and check-ins, set notifications and appointment reminders, and send their assigned participants direct messages that will show up only on that participant's profile. PNs will also be able to view women's responses in the real time data on medication and appointment outcomes, to inform their upcoming session and/or check-in. In addition to video conference/phone sessions and check-ins, participants will receive automated daily medication reminder text messages, scheduled appointment alerts, and access daily postings in the education and self-care tips component of the app.

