## Statistical Analysis Plan

The statistical plan includes measuring feasibility of delivering the intervention, the acceptability of the LinkPositively intervention, and the impact of the intervention.

**Feasibility** The first step in assessing feasibility of delivering the intervention was by creating a Consort flow diagram tracking screening, eligibility, decision to participate, participation at baseline, and participation at 3-month and 6-month follow-ups. The second step in assessing feasibility was to compute the percentage of participants at baseline who were retained at 3-month follow-up and 6-month follow-up, and comparing proportion trends between the intervention and control groups. We used the following retention cut-off percentages to assess feasibility: a) 90+% = strong feasibility; b) 80-89% = acceptable feasibility; c) 70-79% = modest feasibility with a need for improvement; d) <70% = unacceptable.

**Acceptability** We assessed acceptability of the intervention by asking participants in the LinkPositively group about: 1) the quality rating of the program/app, 2) whether or not they received the type of program/app they were anticipating, 3) to what extent the program/app met their needs, 4) whether or not they would recommend the program/app, 5) level of satisfaction with the help received; 6) whether or not the program helped them deal more effectively with their problems, 7) level of satisfaction with the program received, and 8) whether or not they would seek help from the program/app again.

These measures of acceptability were assessed at both 3-month and 6-month follow-ups. At each timepoint, we computed mean scores and standard deviations, as well as median scores and interquartile ranges, for all continuous variables. We calculated frequency and percentages for all categorical variables.

**Intervention Impact** To estimate the preliminary effect of the intervention on primary outcomes we examined differences by group (intervention vs control) in responses to HIV care outcomes over time, ART adherence over time, and mental health outcomes over time. Responses were collected at baseline, 3-month follow-up, and 6-month follow-up. Due to the small n's, we calculated median scores and interquartile ranges for all continuous variables, and frequency/percentages for categorical variables. These statistics were stratified by group, and trends were compared, but significance could not be calculated due to low power.

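### The SAP grades study retention as feasibility of delivering the intervention and leaves the planned intervention use data unanalysed

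*Combined protocol and SAP*

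**What the plan says.** The SAP names feasibility of delivery as its first objective and assesses it in two steps.

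- **Step 1** is a participant flow: "The first step in assessing feasibility of delivering the intervention was by creating a Consort flow diagram tracking screening, eligibility, decision to participate", followed by participation at baseline, 3 months and 6 months. No grade is attached.
- **Step 2** is to "compute the percentage of participants at baseline who were retained at 3-month follow-up and 6-month follow-up", while "comparing proportion trends between the intervention and control groups".

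The grading rule follows: "We used the following retention cut-off percentages to assess feasibility". The bands are 90% and over (strong), 80–89% (acceptable), 70–79% (modest, needing improvement) and below 70% (unacceptable).

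The protocol had set a wider task. Section 6, Aim 2, says: "Intervention use data will be collected throughout the intervention period to examine feasibility, acceptability, and the associations between components used and study outcomes". Section 9, under Virtual Peer Navigation, describes a source for session data: "In the backend of the website app, PNs will enter case notes on PN sessions and check-ins". The same section describes the control arm as receiving "self-directed (non-Peer Navigation supported) treatment as usual".

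**The concern.** Retention at study visits and delivery of an intervention are different quantities. A woman can attend every visit, complete the survey and give hair samples without opening the app or meeting her navigator. The incentives to attend do not depend on use. The visit payments ($25, $30 and $40), the $10 completion bonus and the $25 per hair sample go to both arms, and the retention tactics in section 9 are not tied to the intervention.

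Feasibility is a stated aim of this pilot, which is meant to prepare for a large-scale R01. A conclusion that delivery was strongly feasible would carry weight in that decision, yet the SAP's rule can produce it when few assigned women used the intervention. Without delivery data, a flat pattern in the descriptive outcomes also cannot be separated from simple non-use.

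**Working it through.** The SAP gives no figure to reproduce on this point, so the check is a comparison of texts followed by short arithmetic.

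**1. Each SAP analysis against the question of what was delivered**

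| SAP element | What it records | Records receipt of the intervention? |
|---|---|---|
| Feasibility step 1 | Screening, eligibility, decision to join, visit participation | No |
| Feasibility step 2 (graded) | Retention at 3 and 6 months, both arms | No |
| Acceptability | Eight opinion items, LinkPositively arm | No; opinions, not counts |
| Impact | Outcomes by randomised group | No |

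Aim 2 gives the use data three purposes: feasibility, acceptability, and association of components used with outcomes. The SAP carries out none of them and refers to no other analysis section.

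**2. What the rule permits.** The planned arms are 40 and 40 (section 10).

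- Pooled: 72/80 = 0.90, graded strong.
- Intervention arm alone: 36/40 = 0.90, graded strong.

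Neither calculation contains a use variable, so the grade is the same at any level of use. If the grade is pooled, 40/80 = 50% of the planned denominator is controls, to whom nothing is delivered.

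**3. The protocol's own expectation.** Section 9 expects at least 85% at the first follow-up and 80% at the second. Read as percentages of those enrolled, these are 0.85 × 80 = 68 and 0.80 × 80 = 64 women, and both fall in the acceptable band. The same gap applies there, because that grade is also independent of use.

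**4. Whether 40 women can support a delivery table.** The Wilson 95% interval for a proportion p is

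[p + z²/2n ± z√(p(1−p)/n + z²/4n²)] / (1 + z²/n), with z = 1.96.

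It is widest at p = 0.5. With n = 40 (20/40), the half-width is (1.96/1.0960) × √(0.00625 + 0.00060) = 0.148, so the interval is 35% to 65%.

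Exact (Clopper–Pearson) intervals over a range of results are below. The proportions are assumed, since the documents give no expected level of use.

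| Women | % | Exact 95% CI |
|---|---|---|
| 20/40 | 50 | 33.8–66.2 |
| 28/40 | 70 | 53.5–83.4 |
| 32/40 | 80 | 64.4–90.9 |
| 36/40 | 90 | 76.3–97.2 |

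The table can tell low delivery from high. It cannot separate neighbouring 10-point bands.

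**5. Denominators.** Section 5 describes "4 weekly one-on-one video sessions", whereas Virtual Peer Navigation in section 9 describes five structured sessions over five weeks. For 40 women that is 40 × 4 = 160 or 40 × 5 = 200 sessions. A woman who completes four is 4/4 = 100% or 4/5 = 80% complete. The Intervention Arm paragraphs also give the number of app components as four in one place and five in another.

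**The case against.** Retention is a standard and legitimate pilot criterion, and the SAP openly calls its bands retention cut-offs, so a reader can see what is graded. Retention is to be compared by arm, which makes the intervention arm visible and gives some indirect information. A natural reading is that the bands apply to each percentage computed, with no pooling. The 90% example lies above the protocol's own expectation of 85% and 80%. Several acceptability items, such as satisfaction with the help received, might reveal widespread non-use. Finally, navigator notes may be free text, so turning them into counts takes work.

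Much of this is fair, and it limits the claim. Retention should stay. The by-arm comparison is worth keeping, though what it says about delivery is weak. The pooled example is not essential, since 36/40 in one arm gives the same grade, and the gap exists at every grade. The SAP does not actually state which arm or visit carries the grade. Opinion items may hint at non-use but do not count sessions or app activity. The effort of abstracting notes is a real cost, and the fix allows for use data not being available. The conflicting session counts are a separate inconsistency in the protocol; they matter here because they set denominators.

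**Conclusion.** The concern holds. The SAP describes its measure as feasibility of delivery, grades only visit retention, and leaves out the use data that Aim 2 committed to examining feasibility. Followed exactly, the rule can give a strong grade at any level of use, whether pooled (72/80) or in the intervention arm alone (36/40).

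This is a defect in what may be concluded. It does not affect randomisation or the outcome data, and it does not suggest that use was low or that the data were not collected. It rests on the SAP text being the full analysis plan and on the planned 40 women per arm. The change should be made, because feasibility is a headline conclusion of the pilot.

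**What to change.** 1. Label the 90/80/70% bands as feasibility of study retention. State the arm (or pooled sample) and the visit to which the grade applies. Keep the comparison by arm.
2. Add one descriptive table for all women randomised to LinkPositively (planned 40), drawn from the use data and navigator notes. Give the number and percentage, with 95% CI, who activated the app, completed the intake, completed each scheduled session and used each component. Base any statement on feasibility of delivery on this table.
3. The SAP is written in the past tense, so label any delivery threshold chosen after data were seen as post hoc. Without a threshold, report descriptively. If the use data are not available, limit the conclusion to study retention.
4. Reconcile the session counts (section 5 against section 9) and the component counts (within section 9) before fixing the denominators.

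The cost is SAP wording and one table for one arm, plus whatever abstraction the case notes need. The data are already planned and no new participant contact is required. The downside is some extra analysis and possibly a less favourable feasibility statement.

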**Quantitative Survey.** The quantitative survey will include the following sections: (1) Demographic questions (e.g. age, biological sex at birth, gender identity, race/ethnicity, education, sexual orientation, marital status, employment, number of children, housing status, medical insurance status, food insecurity); (2) Socioeconomic status; (3) Mental health and behavioral health history (e.g. depression, anxiety, alcohol and substance use diagnosis and/or abstinence, lifetime history of trauma); (4) HIV care and treatment history (e.g. obtaining medical care, usual source of medical care, treatments, medications, insurance status, barriers to HIV treatment, self-reported adherence, adherence self-efficacy); (5) Support and Coping (e.g. social support, coping self-efficacy, ancillary support utilization); (6) Health care interactions (e.g. HIV stigma, medical mistrust) (7) Syndemic factors (e.g. interpersonal violence). [See Quantitative Survey].

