## 14. POTENTIAL RISKS

### **Potential Risks**

The risks associated with participation in the study are primarily psychological, given the nature of factors associated with Black WLHA with a history of interpersonal violence. These risks are discussed below:

**Psychological Risks:** In the treatment group (intervention arm), participants may experience psychological distress while talking about issues (e.g., adverse mental health, intimate partner violence, HIV disclosure) raised during one-on-one sessions with virtual peer navigators and phone/text check-ins. Distress may also occur when participants are not interacting with the virtual peer navigator. In the standard of care group (control arm), participants may also experience distress. Participants will be asked questions about mental health and intimate partner violence. As a result, participants may be uncomfortable or experience stress or emotional pain in responding to these questions. Participating in the intervention could also lead to self-awareness about the limitations of one's knowledge of HIV care and treatment, as well as barriers (e.g., substance use, adverse mental health, discrimination, etc.). Participants may also disclose their HIV status for the first time to peers who are enrolled and interacting on the social networking platform, which may cause psychological distress.

**Physical Risks:** We will collect hair samples at 3- and 6-month follow-up assessments, which could cause some physical discomfort. However, the amount of hair collected is equivalent to the daily amount of hair strands that are lost and the hair sample collection procedure itself is considered noninvasive. All research staff members will be trained by [name] (Consultant) in hair sample collection procedures. Confidentiality: There is potential for violation of participant confidentiality if others find out about participants' HIV status or study participation. In addition, women who may be in an abusive relationship, may be concerned that their partner will find out about their participation in the intervention. For eligible participants, as a result of participating in this study, it is possible that these participants may be identified by others, including law enforcement, such as those who may be a victim or perpetrator of violence.

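### Mental health is summarised only at arm level, so worsening in a minority of women, the harm the protocol chiefly warns of, could easily go unseen in the planned summaries

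*Combined protocol and SAP*

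**What the plan says.** Protocol section 14 (Potential Risks) states: "The risks associated with participation in the study are primarily psychological". For the intervention arm it says that "participants may experience psychological distress while talking about issues" in the peer navigator sessions and check-ins. It also mentions distress from disclosing HIV status for the first time on the social networking feed. Section 9 shows that the navigator sessions deal with trauma and with PTSD after violence.

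The survey in section 9 (Quantitative Survey) is given to both arms at baseline, month 3 and month 6. One of its parts is "Mental health and behavioral health history (e.g. depression, anxiety, alcohol and substance use diagnosis and/or abstinence, lifetime history of trauma". The survey itself, with its instruments and cut-offs, is not in the text available for this review.

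The SAP sets its scope as follows: "The statistical plan includes measuring feasibility of delivering the intervention, the acceptability of the LinkPositively intervention, and the impact of the intervention". Mental health appears under Intervention Impact, in the phrase "ART adherence over time, and mental health outcomes over time". The summaries there are: "we calculated median scores and interquartile ranges for all continuous variables, and frequency/percentages for categorical variables". On the comparison it says "These statistics were stratified by group, and trends were compared", and that "significance could not be calculated due to low power". It describes no change from a woman's own baseline, no count of women who worsened, and no range or other tail summary.

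Section 15 describes staff monitoring of adverse events, severity grading and periodic aggregate review. It does not link survey scores to that review or mention a comparison by arm.

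**The concern.** A programme that helps most women a little and distresses a few is the pattern section 14 warns of. Arm-level medians and percentages net the two groups against each other. A median need not move when a minority gets worse. A percentage above a cut-off is unchanged when equal numbers cross in each direction. The plan could therefore report stable or better mental health in the LinkPositively arm while some women deteriorated. The pilot is meant to prepare a large-scale R01, so a missed signal would carry into that design.

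**Working it through.** The plan states no power, SD or effect size, so there is no figure of its own to reproduce.

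**Inputs from the documents.** 40 women per arm. Expected retention is 85% at month 3 (0.85 × 40 = 34) and 80% at month 6 (0.80 × 40 = 32, or 0.80 × 34 ≈ 27 if the second rate applies to those still present). I use 32; results at 34 and 27 are similar.

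**Assumptions, not in the documents.** Normal scores in baseline SD units, higher = worse. Visit correlation ρ of 0.6 or 0.8. A share f = 5/32 = 0.156 worsens by D and the rest shift by g. The control arm does not change on average.

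**Step 1: a case that needs no distribution.** With 32 women the median lies between ranks 16 and 17, and the upper quartile between ranks 24 and 25. If the 6 highest scorers (ranks 27 to 32) each worsen by 1.5 SD and nobody else changes, neither the median nor the upper quartile moves at all.

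**Step 2: expected shift in the median.** The new median m solves f·Φ(m − D) + (1 − f)·Φ(m − g) = 0.5.
- D = 1, g = −0.2, m = −0.037: 0.156 × 0.150 + 0.844 × 0.565 = 0.023 + 0.477 = 0.500. The arm looks slightly better.
- D = 1.5, g = −0.2, m = 0.00: 0.156 × 0.067 + 0.844 × 0.579 = 0.010 + 0.489 = 0.499. No visible change.

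**Step 3: how often chance carries a woman past a threshold.** The SD of individual change is √(2(1 − ρ)), which is 0.894 at ρ = 0.6 and 0.632 at ρ = 0.8. For a woman with no true change:
- at least 1 SD worse: 1 − Φ(1/0.894) = 13%; 1 − Φ(1/0.632) = 6%
- at least 0.5 SD worse: 1 − Φ(0.5/0.894) = 29%; 1 − Φ(0.5/0.632) = 21%

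**Step 4: arm-level summaries against a within-woman count.** Simulation, 40,000 replicates, 32 per arm. The median and upper quartile columns are intervention minus control in change from baseline, with standard errors in brackets. The count columns are intervention against control.

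| Setting | Median | Upper quartile | Worse by ≥0.5 SD | Worse by ≥1 SD |
|---|---|---|---|---|
| 5 worse by 1, 27 better by 0.2, ρ 0.6 | −0.04 (0.33) | +0.03 (0.37) | 29% v 29% | 15% v 13% |
| 5 worse by 1.5, 27 better by 0.2, ρ 0.6 | 0.00 (0.34) | +0.13 (0.38) | 32% v 29% | 19% v 13% |
| 5 worse by 1.5, 27 better by 0.2, ρ 0.8 | 0.00 (0.28) | +0.13 (0.32) | 26% v 21% | 15% v 6% |
| 5 worse by 1, 27 unchanged, ρ 0.6 | +0.14 (0.33) | +0.19 (0.37) | 35% v 29% | 19% v 13% |

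Check of row 2, last column: [5 × Φ(0.5/0.894) + 27 × (1 − Φ(1.2/0.894))]/32 = (5 × 0.712 + 27 × 0.090)/32 = 5.98/32 = 19%.

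The intervention arm looks no worse than control on the median in 54%, 50%, 50% and 34% of trials (rows 1 to 4). On the 1 SD count the shares are 46%, 31%, 10% and 32%.

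**Step 5: percentage above a cut-off.** With an illustrative cut-off at +0.5 SD and 6 women worse by 1.5 SD, the percentage rises by about 10 points if the others do not change, but by only 2 points if they improve by 0.3 SD (standard error 11 to 13 points in both cases).

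**Step 6: precision of the count.** For 6/32 against 2/32 the difference is 12.5 points, with a 95% CI of about −5 to +30. Power for 20% against 5% at 32 per arm is about 44%.

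**The case against.** Four points on the other side have weight.

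- **The planned summaries are not blind.** The SAP reports the IQR as well as the median. If the other women do not improve, the median, the upper quartile and a cut-off percentage all shift the right way. A reader might infer that the harm would never show. The documents do not support that; it depends on how far improvement elsewhere offsets it.
- **Adverse-event monitoring is a second route.** Section 15 provides staff observation, graded events and aggregate review, and acute distress in a session may surface there. Section 14 also refers to a data and safety monitoring plan that is not in the text available for this review. One cannot conclude that psychological harm goes unmonitored or untabulated outside the SAP. The point concerns the SAP's mental health summaries only.
- **Survey scores are not the same as session distress.** The structured sessions run over five weeks and the surveys come at months 3 and 6. Some survey items are histories or diagnoses that cannot yield a change score. The fix must be limited to scales repeated at baseline and follow-up.
- **A count is no cure-all.** It is tempting to suppose that it would pick out exactly the 5 of 32 women affected. It would not, because it counts observed change, and chance change is common. At 0.5 SD it does no better than the median in row 1. At 1 SD it helps clearly when the deterioration is large and the others improve (rows 2 and 3), and little otherwise (rows 1 and 4).

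Low power is a weaker objection, since the SAP is descriptive throughout and the addition would be too.

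**Conclusion.** The concern holds in a limited form. The protocol names psychological distress as its main risk, and the SAP has no summary of mental health change within women. If most women improve slightly while about 16% worsen by 1 to 1.5 SD, the expected difference in medians is −0.04 to 0.00 SD, and the upper quartile moves by well under one standard error. Deterioration in a minority could then easily go unseen in these summaries. A within-woman count at 1 SD, set against control, improves the chance of seeing it without making detection reliable. All the sizes rest on assumed normal scores, visit correlation, and size and share of worsening; the documents give none of these. This is an inexpensive improvement to the SAP. It is not evidence that harm occurred.

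**What to change.** For each mental health scale measured at baseline and follow-up, add a descriptive safety table by arm at months 3 and 6, with:

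- the number of women with both visits
- the distribution of within-woman change (median, IQR and range, or an individual change plot)
- the number and percentage worsening by a large prespecified amount, for example at least 1 baseline SD or newly crossing the scale's own cut-off, with exact 95% CIs
- the between-arm difference with its 95% CI

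State that the count is to be read only against the control arm, since about 6 to 13% of women would pass 1 SD by chance under the assumed correlations. A 0.5 SD threshold is too small, because chance alone carries 21 to 29% past it. Keep the medians and percentages as the impact summary. The SAP is written in the past tense, so if the data have already been examined, label the threshold post hoc.

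The cost is one table, and perhaps a plot, from data already collected. The intervals will be wide, the result is descriptive only, and the mental health findings may look less favourable.
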